9.2. Adverse Event Collection and Reporting

In the event of a medical emergency, the Investigator at the clinical site will institute any medical procedures deemed appropriate. A 24-hour Urgent Medical Contact will be provided to contact the Medical Monitor for further guidance.

Sites will receive a contact card where the following numbers (24-hour Urgent Medical Contact) are provided:

PPD (primary number)
PPD (alternative number)

The medical call center will contact Medical Monitor for the assigned region.

All AEs (see Section 9.4.1 for definitions) occurring after the subject signs the ICF and up to 30 days after the last dose of study drug (ie, the Follow-Up Visit), whether observed by the Investigator or reported by the subject, will be recorded on the Adverse Event CRF page. Medical conditions (including laboratory values/vital signs that are out of range) that were diagnosed or known to exist prior to Informed Consent will be recorded as part of medical history.

All AEs, serious adverse events (SAEs), bleeding, and events of special interest are to be reported according to the procedures in Section 9.5.

All laboratory results and vital signs should be appraised by the Investigator to determine their clinical significance. Isolated abnormal laboratory results or vital sign findings should be reported as AEs if they are symptomatic, lead to study drug discontinuation, lead to dose reduction, require corrective treatment, or constitute an AE in the Investigator's clinical judgment.

At each visit, the Investigator will determine whether any AEs have occurred by evaluating the subject. Adverse events may be directly observed, reported spontaneously by the subject or by questioning the subject at each study visit. Subjects should be questioned in a general way, without asking about the occurrence of any specific symptoms. The Investigator must assess all AEs to determine seriousness, severity, and causality, in accordance with the definitions in Section 9.4. The Investigator's assessment must be clearly documented in the site's source documentation with the Investigator's signature.

The Investigator must always report the diagnosis as the AE or SAE term. When a diagnosis is unavailable, report the primary sign or symptom as the AE or SAE term with additional details included in the narrative until the diagnosis becomes available. If the signs and symptoms are distinct and do not suggest a common diagnosis, report them as individual entries of AE or SAE.

For events that are serious due to hospitalization, the reason for hospitalization must be reported as the SAE (diagnosis or symptom requiring hospitalization). A procedure is not an AE or SAE, but the reason for the procedure may be an AE or SAE. Pre-planned (prior to signing the ICF) procedures or treatments requiring hospitalization for pre-existing conditions that do not worsen in severity should not be reported as SAEs (see Section 9.4.2 for definitions).

For deaths, the underlying or immediate cause of death should always be reported as an SAE.

Any serious, untoward event that may occur subsequent to the reporting period that the Investigator assesses as related to study drug should also be reported and managed as an SAE.

The Investigator should follow subjects with adverse events until the event has resolved or the condition has stabilized. In case of unresolved adverse events, including significant abnormal laboratory values at the end of study assessment, these events will be followed until resolution or until they become clinically not relevant.

9.3. Adverse Events of Special Interest

9.3.1. Liver Enzyme Abnormalities/Liver Dysfunction

Liver function is an area of special interest. Critical liver laboratory assessments include ALT, AST, TBL, and ALP. Particular attention will be paid to subjects with ALT and/or AST \geq 3 × ULN and TBL \geq 2 × ULN simultaneously without evidence of cholestasis (ALP \geq 2 × ULN is considered evidence of possible cholestasis) and without alternative etiology for hepatocellular damage.

Liver enzyme abnormalities that lead to study drug interruption/discontinuation as well will be adjudicated in a blinded manner by the CEC. The CEC charter includes a process by which selected cases will be adjudicated by a liver disease specialist.

In cases of liver laboratory abnormalities, it is important to ensure that the nature and the extent of liver injury is identified and study subjects are monitored until the liver laboratory assessments return to normal.

If the subject discontinued study drug due to liver enzyme abnormalities, the subject will have additional evaluations in order to determine the nature and severity of the liver injury. The documents to be sent for adjudication:

- Results of confirmatory tests and diagnostic evaluation
- The hepatic event adjudication worksheets.

If a subject temporarily interrupts (or discontinues) study drug due to confirmed liver enzyme abnormalities or jaundice, the subject will have additional evaluations as described in Section 5.6.3 at the discretion of the Investigator.

Combined elevations of aminotransferases and bilirubin, either serious or non-serious and whether or not causally related, meeting the clinical laboratory criteria of a potential Hy's Law case [ALT or AST \geq 3 × ULN with simultaneous TBL \geq 2 × ULN] should always be reported to the Sponsor using a Serious Adverse Events Reporting form, in addition to reporting it in eCRF, with the Investigator's assessment of seriousness, causality, and a detailed narrative. These events should be reported within 24 hours of Investigator's awareness of the event.

An Independent Data Monitoring Committee (IDMC) may recommend termination of the study. Termination may be made for any of the following reasons:

- Concerns about significantly higher bleeding risk relative to 1 of the study arms,
- Concerns about drug-induced liver injury,
- Any other safety concerns based on benefit/risk evaluation by the IDMC.

If the subject discontinues study drug due to liver enzyme abnormalities, the subject will have additional clinical and laboratory evaluations until clinically acceptable resolution in order to determine the nature and severity of the potential liver injury.

9.4. Adverse Event

9.4.1. Definition of Adverse Event

An adverse event is any untoward medical occurrence in a subject administered a pharmaceutical product and that does not necessarily have to have a causal relationship with this treatment. An AE can therefore be any unfavorable and unintended sign (including an abnormal laboratory finding, for example), symptom, or disease temporally associated with the use of a medicinal product, whether or not considered related to the medicinal product (ICH E2A Guideline. Clinical Safety Data Management: Definitions and Standards for Expedited Reporting, Oct 1994).

It is the responsibility of Investigators, based on their knowledge and experience, to determine those circumstances or abnormal laboratory findings which should be considered adverse events.

9.4.2. Serious Adverse Event

A SAE is any untoward medical occurrence that at any dose:

- Results in death,
- Is life-threatening,
- Requires inpatient hospitalization or prolongation of existing hospitalization,
- Results in persistent or significant disability/incapacity,
- Is a congenital anomaly/birth defect, or
- Is an important medical event.

Note: The term "life-threatening" in the definition of "serious" refers to an event in which the subject was at risk of death at the time of the event; it does not refer to an event which hypothetically might have caused death if it were more severe (ICH E2A Guideline. Clinical Safety Data Management: Definitions and Standards for Expedited Reporting, Oct 1994).

Medical and scientific judgment should be exercised in deciding whether expedited reporting is appropriate in other situations, such as important medical events that may not be immediately life-threatening or result in death or hospitalization but may jeopardize the subject or may require intervention to prevent one of the other outcomes listed in the definition above. Examples include allergic bronchospasm, convulsions, and blood dyscrasias or development of drug dependency or drug abuse.

Note:

- Procedures are not AEs or SAEs, but the reason for the procedure may be an AE or SAE.
- Pre-planned (prior to signing the ICF) procedures or treatments requiring hospitalizations for pre-existing conditions that do not worsen in severity are not SAEs.

9.4.3. Severity Assessment

The following definitions should be used to assess intensity of adverse events:

- Mild: Awareness of sign or symptom, but easily tolerated, ie, does not interfere with subject's usual function.
- Moderate: Discomfort enough to cause interference with usual activity.
- Severe: Incapacitating with inability to work or do usual activity, ie, interferes significantly with subject's usual function.

Severity vs. Seriousness: Severity is used to describe the intensity of a specific event while the event itself, however, may be of relatively minor medical significance (such as severe headache). This is not the same as "seriousness," which is based on subject/event outcome at the time of the event.

9.4.4. Causality Assessment

The Investigator should assess causal relationship between an adverse event and the study drug or drugs if a combination is administered on the basis of his/her clinical judgment and the following definitions. The causality assessment must be made based on the available information and can be updated as new information becomes available.

• Related:

The AE follows a reasonable temporal sequence from study drug administration, and cannot be reasonably explained by the subject's clinical state or other factors (eg, disease under study, concurrent diseases, and concomitant medications).

Or

The AE follows a reasonable temporal sequence from study drug administration, and is a known reaction to the drug under study or its chemical group, or is predicted by known pharmacology.

• Not Related:

The AE does not follow a reasonable sequence from study drug administration, or can be reasonably explained by the subject's clinical state or other factors (eg, disease under study, concurrent diseases, and concomitant medications).

9.4.5. Action Taken Regarding Study Drug(s)

Dose Not Changed: No change in study drug dosage was made.

Drug Withdrawn: The study drug was permanently stopped.

Dose Reduced: The dosage of study drug was reduced.

Drug Interrupted: The study drug was temporarily stopped.

Dose Increased: The dosage of study drug was increased.

Not Applicable: (eg, subject died, study treatment had been completed prior to reaction/event, or reaction/event occurred prior to start of treatment

9.4.6. Other Action Taken for Event

None: No treatment was required.

Medication required: Prescription and/or over-the-counter medication was required to treat the adverse event.

Hospitalization or prolongation of hospitalization required: Hospitalization was required or prolonged due to the AE, whether or not medication was required.

Other.

9.4.7. Adverse Event Outcome

• Recovered/Resolved

The subject fully recovered from the adverse event with no residual effect observed.

• Recovering/Resolving

The adverse event improved but has not fully resolved.

• Not Recovered/Not Resolved

The adverse event itself is still present and observable.

• Recovered/Resolved with Sequelae

The residual effects of the adverse event are still present and observable.

Include sequelae/residual effects.

• Fatal

Fatal should be used when death is a direct outcome of the adverse event.

• Unknown

9.5. Serious Adverse Events and Adverse Event of Special Interest Reporting – Procedure For Investigators

All AEs, SAEs, and adverse events of special interest including efficacy and safety endpoints that will be adjudicated will be reported in the CRF.

In the event of a Medical Emergency, the Investigator at the clinical site will institute any medical procedures deemed appropriate. A 24-hour Urgent Medical Contact will be provided to contact the Medical Monitor for further guidance.

Sites will receive a contact card where the following numbers (24-hour Urgent Medical Contact) are provided:

PPD (primary number) PPD (alternative number)

The medical call center will contact Medical Monitor for the assigned region.

Fatal or life-threatening serious events that are also efficacy or safety endpoints will be reported as an expedited report to the regulatory agencies. Events such as MI, SEE, stroke, VTE, and PE and/or safety endpoints such as bleeding events (which are not life-threatening or fatal) will be exempted from SAE processing and expedited reporting. Efficacy and safety endpoints will be captured on specifically designed eCRFs. These events are clinically anticipated events in the target treatment population, and will be periodically reviewed by the IDMC to ensure prompt identification of any clinically concerning safety issues.

The following types of events should be reported by the Investigator on a Serious Adverse Event Report form within 24 hours of awareness:

- SAEs (see Section 9.4.2 for definition), including life-threatening or fatal bleeds.
- All SAEs resulting in death, regardless of whether they are waived endpoints for processing and expedited reporting, will be processed by the CRO for entry into the Sponsor's global safety database.
- Hepatic events meeting combination abnormalities [ALT or AST $\ge 3 \times$ ULN with simultaneous TBL $\ge 2 \times$ ULN] (potential Hy's Law case), both serious and non-serious (see Section 9.3.1 for additional details).

All events (serious and non-serious, including efficacy and safety endpoint events) must be reported with Investigator's assessment of the event's seriousness, severity, and causality to the study drug. A detailed narrative for SAE or hepatic events meeting the criteria, summarizing the course of the event, including its evaluation, treatment, and outcome should be provided. Specific or estimated dates of event onset, treatment, and resolution should be included when available. Medical history, concomitant medications, and laboratory data that are relevant to the event should also be summarized in the narrative. For fatal events, the narrative should state whether an autopsy was or will be performed, and include the results if available. Source documents (including medical reports) will be retained at the clinical site and should not be submitted to the Sponsor for SAE reporting purposes.

Urgent safety queries must be followed up and addressed promptly. Follow-up information and response to non-urgent safety queries should be combined for reporting to provide the most complete data possible within each follow-up.

See Section 15.12 for contact information for SAE reporting. Please call your study monitor for any questions on SAE reporting.

9.6. Notifying Regulatory Authorities, Investigators, and Institutional Review Board/Ethics Committee

Daiichi Sankyo Inc. and/or CRO will inform Investigators, Institutional Review Boards/Ethics Committees (IRBs/ECs), and regulatory authorities of any suspected unexpected serious adverse reactions (SUSARs) occurring in other clinical sites or other studies of the study drug, as appropriate per local reporting requirements. Daiichi Sankyo Inc. and/or CRO will comply with any additional local safety reporting requirements. In the United States, upon receipt of the Sponsor's notification of SUSARs that occurred with the study drug, unless delegated to the Sponsor, it is the Investigator's responsibility to inform the IRB per Sponsor's instruction.

In the European Economic Area states, it is the Sponsor's responsibility to report SUSARs to all ECs.

9.7. Exposure In Utero During Clinical Studies

Daiichi Sankyo Inc. must be notified of any subject who becomes pregnant while receiving or within 30 days of discontinuing the study drug.

Although pregnancy is not technically an adverse event, all pregnancies must be followed to conclusion to determine their outcome. This information is important for both drug safety and public health concerns. It is the responsibility of the Investigator, or designee, to report any pregnancy in a female subject using the exposure in utero (EIU) reporting form. Please contact your study monitor to receive the EIU Reporting Form upon learning of a pregnancy. The Investigator should make every effort to follow the subject until completion of the pregnancy and complete the EIU Reporting Form with complete pregnancy outcome information, including normal delivery and induced abortion. The adverse pregnancy outcome, either serious or nonserious, should be reported in accordance with study procedures. If the outcome of the pregnancy meets the criteria for immediate classification as a SAE (ie, post-partum complications, spontaneous or induced abortion, stillbirth, neonatal death, or congenital anomaly, including that in an aborted fetus), the Investigator should follow the procedures for reporting SAEs outlined in Section 9.5.

9.8. Clinical Laboratory Evaluations

To expedite qualification and randomization for subjects living a distance from the Investigator site, the site may choose to use their local laboratory for screening eligibility labs. The sample should be split with analysis at both the central laboratory as well as the local laboratory. For the purpose of eligibility, the local laboratory results will be utilized and entered into the eCRF.

Blood and urine samples (if abnormal by dipstick) for clinical laboratory evaluations will be shipped to a central laboratory for analysis. Results of all clinical laboratory tests will be reported in the subject's eCRF or merged electronically with the clinical database.

9.8.1. Hematology

The ethylenediaminetetraacetic acid tube of blood will be drawn for the hematology assessments listed in. These will be measured from samples obtained at the Screening/Qualification visit (Visit 1), Month 3 (Visit 5), and Month 12/Discontinuation Visits (Visit 8).

Table 9.1: Hematology Analyses

Hemoglobin

Hematocrit

Red blood cell (RBC) count (with indices)

White blood cell (WBC) count

Platelet count

9.8.2. Blood Chemistry

A serum separating tube of blood will be drawn for the blood chemistry assessments listed in Table 9.2 and performed at the Screening Visit.

Serum creatinine will also be measured on Month 1, 3, 6, 9, and Month 12/Discontinuation Visits.

Table 9.2:Serum Chemistry

Sodium	Creatinine ^a
Potassium	Blood urea nitrogen
Bicarbonate	Alkaline phosphatase

^a Serum creatinine will be measured at Screening and On-Treatment Study Visits (Months 1, 3, 6, 9 and Month 12/Discontinuation)

9.8.3. Liver Function Test

The LFT will include alanine aminotransferase (ALT), aspartate aminotransferase (AST), TBL, and ALP. The LFT will be measured at Screening and on-treatment study visits at Months 1 (Visit 3), 3 (Visit 5), and 12 (Visit 8).

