5. STUDY TREATMENT(S)

5.1. Assigning Subjects to Treatments and Blinding

5.1.1. Treatment Groups

All subjects will be assessed for eligibility in the study in accordance with the inclusion/exclusion criteria. Eligible subjects will be stratified and randomized as follows:

• All eligible subjects will be stratified by:

Type of underlying heart disease:

Kawasaki disease

Fontan surgery

Heart failure (HF)

Others (which can include post-surgical procedures for congenital heart disease other than Fontan surgery)

Subjects with underlying disease other than Kawasaki will be further stratified by concomitant use of low dose aspirin (1 to 5 mg/kg/day).

• Randomized in a 2:1 ratio (edoxaban:SOC, respectively) into 1 of 2 treatment arms:

Edoxaban-treatment arm: subjects will receive a selected dose of edoxaban

OR

SOC-treatment arm: subjects will receive SOC anticoagulant according to clinical site's SOC treatment, as follows (alone or in combination):

Heparin, including UFH or LMWH

Vitamin K antagonist (VKA) with potential bridging with heparin based therapy until VKA INR is in therapeutic range

After Month 3, all subjects who continue in the Extension Period and are on SOC will be offered edoxaban treatment and dosed according to their cohort age at the time of subject consent. During the extension period of the study, check the body weight prior to dosing and adjust dosage accordingly. Frequency of dosage changing is up to the Investigator's discretion.

Subjects from 1 to <18 years of age will be enrolled in the study as soon as the dosing regimen is established for each age cohort in the Phase 1 single-dose U157 study.

Additionally, subjects less than 1 year of age will be admitted to the study after review by the IDMC of safety data of 50% of subjects in the 1 to <18 years of age group who have completed the Main Treatment Period of 3 months (50 subjects in edoxaban arm and 25 subjects in SOC arm).

Subjects younger than 6 years of age will only receive edoxaban granules for oral suspension, which will give more flexibility to adjust mg/kg dose. Doses for all age groups will be selected to elicit target exposures comparable to those achieved from the adult Phase 3 study of 60 mg.

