6.5.1. Month 6 (Visit 6) Procedures

- Record concomitant medications
- Count unused study drug tablets/bottles to assess compliance
- Dispense study drug medication and review dosing instructions
- Perform physical examination (Section 9.9) including:

Vital signs (BP, heart rate, and body temperature after resting in a sitting or supine position [Note: the appropriate cuff size base on arm circumference will be used.])

Height and body weight (may be performed by an Investigator or other healthcare provider designated by the Investigator).

- Urine pregnancy test for females of child bearing potential
- Review for symptomatic endpoint events (bleeding, symptomatic TE with appropriate imaging)
- Safety review for AEs/SAEs
- Collect blood samples for the following laboratory tests:

Serum creatinine test

eGFR assessment

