6.5.2. Month 9 (Visit 7) Procedures

- Record concomitant medications
- Count unused study drug tablets/bottles and calculate compliance
- Dispense study drug medication and review dosing instructions
- Perform physical examination (Section 9.9) including:

Vital signs (BP, heart rate, and body temperature after resting in a sitting or supine position [Note: the appropriate cuff size base on arm circumference will be used.]

Height and body weight (may be performed by an Investigator or other healthcare provider designated by the Investigator).

- Urine pregnancy test for females of child bearing potential
- Review for symptomatic endpoint events (bleeding and TE)
- Safety review for AEs/SAEs
- Collect blood samples for the following laboratory tests:
 - Serum creatinine

eGFR assessment

6.5.3. Month 12/Discontinuation Visit (Visit 8; Appropriate for subjects completing Month 12 or treated beyond Month 3 and discontinuing study prior to Month 12)

Discontinuation from study visit will only be required for those extended into the study beyond Month 3 because all subjects are to have study procedures through Month 3.

Procedures for subjects who withdraw consent from the study or are discontinued from the study treatment for any reason are discussed in Section 5.6.

All randomized subjects extended beyond Month 3 who wish to discontinue treatment and study will have Discontinuation Visit (Visit 8) performed when the last dose of study drug is administered after Month 3.

The following will be performed at this visit:

- Record concomitant medications
- Count unused study drug tablets/bottles and calculate compliance
- Perform physical examination (Section 9.9) including:

Vital signs (BP, heart rate, and body temperature after resting in a sitting or supine position [Note: the appropriate cuff size base on arm circumference will be used.])

- Safety review for AEs/SAEs
- Review for symptomatic endpoint events (bleeding and TE)
- Collect blood samples for the following laboratory tests:

LFTs (ALT, AST, TBL, and ALP)

Serum creatinine

eGFR assessment

Hematology

- Urine pregnancy test for females of child-bearing potential
- Optional echocardiogram to evaluate presence of asymptomatic intracardiac thrombosis based on Investigator's discretion.

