11.4.3.2. Analysis of Hepatic Events

The analysis of hepatic events will be based on CEC adjudication results. All CEC adjudication confirmed hepatic events will be summarized for the characteristics of the hepatic events by treatment group for the Main Treatment Period and for the Extension Period.

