	Qualification Visit ^a		Main	Treatment	Period	Ext	ension Perio	d (Optional)	Follow-Up Visit ^b
Visit Number	1	2	3	4	5	6	7	8	9
Study Day	At least Day -30 to Day 1	Day 1	Month 1	Month 2	Month 3	Month 6	Month 9	Month 12/ Discontinuation Visit ^c	30 Days After Last Dose of Study Drug or Discontinuation Visit
Visit Window ^d			±5	±5	±5	±5	±5	±5	±5
IXRS Transaction	Х		X	X	Х	Х	X	Х	
IXRS Randomization		Х							
Study Informed Consent	Х								
Review Inclusion/ Exclusion Criteria	X								
Record Demographic Information	Х								
Record Medical/Surgical History	Х								
Record Prior and Concomitant Medications	X ^e	Х	Х	Х	Х	Х	Х	X	X
Perform Physical Examination (Vital signs and Body Height/Weight Assessments) ^f	X		Х	Х	Х	Х	Х	X	
Measure Body Weight Only		Х							
Liver function assessment (ALT, AST, TBL, ALP) ^g	X		Х		X			Х	
Serum Creatinine/eGFR assessment	X		X		X	X	X	X	
Serum Chemistry Panel excluding creatinine	Х								

Table 17.1:Schedule of Events

Study Period	Screening/	Randomization ^a			On-Treat	ment Study	Visits		Required 30-Day
	Qualification Visit ^a		Main	Treatment	Period	Exte	ension Perio	d (Optional)	Follow-Up Visit ^b
Visit Number	1	2	3	4	5	6	7	8	9
Study Day	At least Day 30 to Day 1	Day 1	Month 1	Month 2	Month 3	Month 6	Month 9	Month 12/ Discontinuation Visit ^c	30 Days After Last Dose of Study Drug or Discontinuation Visit
Visit Window ^d			±5	±5	±5	±5	±5	±5	±5
Screening: aPTT, INR ^h	X ^h								
Post-randomization: INR, Anti-FXa, aPTT, Assessment on SOC ⁱ			X	C					
Echocardiogram ^j	Х				Х			Optional X	
Hematology	X				Х			Х	
Urinalysis	Х								
Urine Pregnancy Test ^k		Х				x			
QOL Questionnaire ¹		Х			X				
AE/SAE Reporting ^m					X		•••••		
Endpoints Reporting (Bleeding, TE) ⁿ				•••••	X	•••••	•••••		
Study Drug Dispensing via IXRS		X	X	X	X	Disper monthly Month optional distrib edoxabar visit i	use on a basis after 3 visit or 3 month ation of a to match aterval	asis after Month 3	
Study Drug Compliance			Λ		Λ	visit or 3 m	at the next sonth drug dis	cheduled visit if pense is used	

Table 17.1:Schedule of Events (Continued)

Study Period	Screening/	Randomization ^a			On-Treat	ment Study	Visits		Required 30-Day
	Qualification Visit ^a		Main	Treatment 1	Period	Exte	ension Perio	d (Optional)	Follow-Up Visit ^o
Visit Number	1	2	3	4	5	6	7	8	9
Study Day	At least Day 30 to Day 1	Day 1	Month 1	Month 2	Month 3	Month 6	Month 9	Month 12/ Discontinuation Visit ^c	30 Days After Last Dose of Study Drug or Discontinuation Visit

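### No liver function test is scheduled between Month 3 and the Month 12/Discontinuation Visit, so children who switch from SOC to edoxaban have none scheduled on the drug before Visit 8, although blood is drawn at Months 6 and 9

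*Combined protocol and SAP*

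**What the plan says.** Section 9.8.3: "The LFT will be measured at Screening and on-treatment study visits at Months 1 (Visit 3), 3 (Visit 5), and 12 (Visit 8". In Table 17.1 the row "Liver function assessment (ALT, AST, TBL, ALP" is marked at Screening, Month 1, Month 3 and Month 12/Discontinuation, and is blank at Months 2, 6 and 9.

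Blood is nevertheless taken in between. Section 9.8.2: "Serum creatinine will also be measured on Month 1, 3, 6, 9, and Month 12/Discontinuation Visits". Section 6.5.1 (Month 6) has the instruction "Collect blood samples for the following laboratory tests", followed only by creatinine and eGFR, and Section 6.5.2 (Month 9) does the same. The visit list for Month 12/Discontinuation (Section 6.5.3) does include "LFTs (ALT, AST, TBL, and ALP".

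On the switch, Section 5.1.1 says: "After Month 3, all subjects who continue in the Extension Period and are on SOC will be offered edoxaban treatment". Section 6.5 lets the investigator add a visit around the switch, but this is discretionary and no LFT is attached to it.

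On the importance of liver findings, Section 9.3.1 says: "Liver function is an area of special interest". Sections 4.3.1 and 15.8 list concern about liver injury from the drug among the reasons for which the IDMC may recommend termination. Section 11.4.3.2 summarises adjudicated hepatic events "by treatment group for the Main Treatment Period and for the Extension Period". Section 11.4.3.4 summarises Extension laboratory values as change from the Month 3 Visit.

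**The concern.** The protocol tests a child randomised to edoxaban 1 month and 3 months after the start of treatment. A child randomised to SOC starts the same drug about 3 months later and gets no equivalent check: the Month 1 and Month 3 LFTs were taken on SOC, and the next scheduled one is Visit 8. No reason is given for the difference.

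What is at stake is ascertainment. The main hepatic criteria in Sections 5.6.3 and 9.3.1 are laboratory thresholds for transaminases and bilirubin. A child without symptoms cannot meet them unless someone orders a test. Between Month 3 and Visit 8 the schedule orders none, so detection of a silent elevation depends on local practice or chance. Liver function is the stated adverse event of special interest, so this is a weak place for the schedule to be silent.

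**Working it through.** The plan gives no figure on this point, so there is none to reproduce. The check is a count of scheduled tests, followed by two illustrations.

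**1. Scheduled LFTs on edoxaban** (Sections 9.8.3 and 6.4.3.1 to 6.5.3, Table 17.1; child completing Month 12)

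| | First LFT on edoxaban | LFTs on edoxaban | Gap after Month 3 |
|---|---|---|---|
| Randomised to edoxaban | Month 1 | 3 (Months 1, 3, 12) | 12 − 3 = 9 months |
| Switched from SOC | Visit 8 | 1 (Month 12) | 12 − 3 = 9 months |

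The 9-month gap applies to every child who completes the Extension. Only the switchers enter it without an earlier LFT on edoxaban. A child who stops early is tested at the Discontinuation Visit, so 9 months is the maximum. With LFTs at Months 6 and 9, a switcher who completes has 3 scheduled tests instead of 1, and the longest gap is 3 months.

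**2. What the Extension analyses receive.** For LFTs, the change from Month 3 in Section 11.4.3.4 has one scheduled later value per child. For a switcher the Month 3 reference was taken on SOC. Section 11.1 summarises all children who take only edoxaban in the Extension as one edoxaban group, so first exposure in switchers is not shown separately.

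**3. Share of edoxaban exposure in the interval.** Inputs: 100 edoxaban and 50 SOC children (Section 11.6), a 3-month Main Treatment Period and an Extension of up to 9 months (synopsis, study duration).

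- Main Treatment Period: 100 × 0.25 = 25 patient-years.
- Extension, all 150 enter and complete: 150 × 0.75 = 112.5. Share: 112.5 / (25 + 112.5) = 82%.
- Half enter and complete (assumed): 75 × 0.75 = 56.25. Share: 56.25 / 81.25 = 69%.
- Half enter and average 4.5 months (assumed): 75 × 0.375 = 28.1. Share: 28.1 / 53.1 = 53%.
- Switchers alone, on the full-completion assumption: 50 × 0.75 = 37.5. Share: 37.5 / 137.5 = 27%.

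**4. Chance that a scheduled LFT falls inside an elevation.** Assumptions, none from the documents: onset uniform over Months 3 to 12, child remains to Month 12, elevation lasts L months (L ≤ 3). With one test the chance is L/9; with three tests it is 3L/9.

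| L (months) | As written | With Months 6 and 9 |
|---|---|---|
| 0.5 | 6% | 17% |
| 1 | 11% | 33% |
| 2 | 22% | 67% |
| 3 | 33% | 100% |

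Uniform onset favours the change. An elevation that begins within a month of the switch and lasts 1 month is over by Month 5 at the latest (3 + 1 + 1) and is missed under both schedules.

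**The case against.** The sections agree with one another, so there is no contradiction to reconcile, and testing frequency is a monitoring choice. The Extension is a single-group, descriptive period; comparisons are confined to the Main Treatment Period (Section 6.4) and the primary endpoint is bleeding. All of that stands: no comparative result changes.

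A reader might infer that the Extension hepatic analysis rests on one end-of-period value. The documents do not support that. Section 11.4.3.2 uses events confirmed by the adjudication committee. These come from abnormalities the investigator identifies (Section 6) or that lead to interruption or discontinuation (Section 9.3.1), whether or not the test was scheduled. Jaundice, and raised transaminases with symptoms, are separate triggers in Section 5.6.3. Only the scheduled LFT summary in Section 11.4.3.4 has a single later value.

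A reader might also take 82% as the expected exposure. It is an upper bound. The Extension is optional, and the global End of Treatment date in Section 3.3 guarantees the last children randomised only 3 months of treatment. Much of the 82% also belongs to children already tested on edoxaban at Months 1 and 3.

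Finally, more LFTs mean more occasions on which the Section 5.6.3 criteria could be met, and no section gives the volume of the Month 6 and Month 9 samples. Section 8.2 makes pharmacodynamic sampling conditional on blood volume, so volume is a recognised constraint. Both points belong in the cost of the change. Neither removes the gap, because an asymptomatic child still has no scheduled test.

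**Conclusion.** The point holds in a limited form, as a low-cost improvement. No LFT is scheduled from after Month 3 until the Month 12/Discontinuation Visit. Up to 50 switchers, if every SOC child enters the Extension and takes edoxaban, have no scheduled LFT on the drug before Visit 8, a wait of up to 9 months. The scheduled LFT summary has one post-Month-3 value per child, set against an on-SOC reference for switchers. The adjudicated hepatic analysis remains open to unscheduled and symptom-driven findings but may under-ascertain asymptomatic or transient elevations.

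The interval holds at most 82% of edoxaban patient-years, and about 53% under the assumption that half enter and average 4.5 months. The detection chances rest wholly on assumed onset and duration and indicate direction only. It would go too far to say that every switcher waits until Month 12, since early stoppers are tested at discontinuation, or that liver injury in the Extension would go unseen.

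**What to change.** Add the existing LFT panel (ALT, AST, TBL, ALP) to the blood draws already scheduled at Months 6 and 9, where blood volume allows. Update Sections 9.8.3, 6.5.1 and 6.5.2 and Table 17.1 together. Leave the interruption and discontinuation rules in Section 5.6.3 as they are.

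The cost is four analytes at two existing draws, with no added visit or venepuncture: a small laboratory charge, possibly more serum from the smallest infants, and more occasions on which the existing Section 5.6.3 criteria could be met. The first added test still falls 3 months after the switch, so the change narrows the gap without reproducing the Month 1 test of the randomised arm. If the sponsor keeps the present schedule, it should give its reason and state the limit on ascertainment alongside Sections 11.4.3.2 and 11.4.3.4.
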